4. ABSTRACT

Name of company: Boehringer Ingelheim			
Name of finished medicinal product: COPD medication of any type			
Name of active ingredient: COPD medication of any type, ATC code R03			
Protocol date: 16 Oct 2019	Study number: 1237-0092	Version/Revision: 1.0	Version/Revision date: Not applicable
Title of study:	Real-world treatment of newly diagnosed COPD patients: A retrospective German claims data analysis		
Rationale and background:	
In terms of COPD drug therapy, the current German COPD guideline (S2) [1, 2] recommends a treatment escalation procedure. For incident COPD patients (for the sake of simplicity, newly diagnosed and so far treatment naïve COPD patients will be referred to as “incident COPD patients” in the following), the German guideline recommends the following:
 
 • No treatment (low symptom burden) • SABA or SAMA • LABA or LAMA or LABA+LAMA. 
All other treatments, particularly combination treatments including ICS¹, are only recommended as escalation therapy.
 
Currently, knowledge on real world treatment of incident COPD patients in Germany is sparse, in particular regarding the frequency of different drug therapy prescriptions and the frequency of early therapy escalation including ICS.
 
This study aims to address this issue by reporting treatment of incident COPD patients in the real world. COPD and treatment associated outcomes, especially severe exacerbations (leading to hospitalization), health-care resource use, and early use of oxygen therapy, will be explored. In addition, real-world treatment of incident COPD patients will be compared to German guidelines, using current 2018 guidelines and 2012 guidelines as framework in two scenario calculations.
		

¹ ICS is recommended by the guideline for COPD patients with an asthmatic component. Based on inclusion/exclusion criteria as applied in this study, these patients will be excluded from analysis.

Name of company: Boehringer Ingelheim			
Name of finished medicinal product: COPD medication of any type			
Name of active ingredient: COPD medication of any type, ATC code R03			
Protocol date: 16 Oct 2019	Study number: 1237-0092	Version/Revision: 1.0	Version/Revision date: Not applicable

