Population:	
The following inclusion criteria apply:
 
 • All patients who were continuously insured by the sickness fund for the entire period (01/01/2013-30/06/2018) or, in case a patient deceased after index date, for the time until death⁴ • A patient will be included as an incident COPD patient if either a hospital documented at least one COPD diagnosis (ICD-10 J 44.-) or a specialist (pneumologist) documented at least 2 confirmed COPD diagnoses (above ICD-10 code) in two different quarters; the first of the above diagnoses is defined as index diagnosis; inclusion period is defined as lasting from 01/01/2014 until 30/06/2017⁵ • Patients should not have received any COPD diagnosis (ICD-10 J44.-) or any COPD-associated medication (Suppl. Table 2⁶) in the 12 months pre-index period • Patient should have, at date of incident COPD diagnosis (index date), an age of at least 40 years 
In the planned analyses, different subpopulations with regard to follow-up time and availability of disease management program (DMP) data will be defined.
		

⁴ Patients censored due to their death will be included as well including reporting of their baseline characteristics.

[figure not shown]
⁵ Please note: Based on all patients with at least one confirmed outpatient or inpatient COPD diagnosis (from specialists, GPs and/or hospitals), an attrition chart will show how many patients are subsequently excluded because of the applied inclusion/exclusion criteria.

⁶ Prescription of systemic/oral corticosteroids (SCS/oral) will not be considered as exclusion criteria

Name of company: Boehringer Ingelheim			
Name of finished medicinal product: COPD medication of any type			
Name of active ingredient: COPD medication of any type, ATC code R03			
Protocol date: 16 Oct 2019	Study number: 1237-0092	Version/Revision: 1.0	Version/Revision date: Not applicable

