9.2 SETTING

An anonymized dataset from the cooperating sickness funds, which includes all patients with at least one COPD diagnosis, who were insured by this sickness funds for the entire period (01/01/2013 - 30/06/2018) will be available.

A patient will be confirmed as being COPD-incident if specialists documented at least two confirmed outpatient COPD diagnoses (ICD J44.-) and/or at least one inpatient COPD diagnosis (ICD J44.-), without such diagnoses in the previous 12 months and without any COPD prescription in the previous 12 months (Suppl. Table 2).

Specific inclusion criteria can be described as follows:

- All patients should have been covered by the sickness fund for the entire period (01/01/2013-30/06/2018) or, in case a patient deceased after index date, for the time until death
- A patient will be included as an incident COPD patient if either a hospital documented at least one COPD diagnosis (ICD-10 J44.-) or a specialist (pneumologist) documented at least two confirmed COPD diagnoses (above ICD-10 code) in two different quarters; the first of the above diagnoses is defined as index diagnosis; inclusion period is defined as lasting from 01/01/2014 until 30/06/2017

- Patients should not have received any COPD diagnosis (ICD-10 J44.-) or any COPD-associated medication (Suppl. Table 2)⁹ in the 12 months pre-index period
- Patient should have, at date of incident COPD diagnosis (index date), an age of at least 40 years

Patients who received at least one confirmed inpatient asthma diagnosis or two confirmed outpatient diagnoses of asthma (ICD-10: J45.-) by pneumologists after the incident COPD diagnosis (index diagnosis) will be separately observed.

Based on these inclusion/exclusion criteria, the following data sets will be analyzed (Figure 3)¹⁰:

- COPD-FULL DATA: All incident COPD patients with a follow-up of up to 54 months
- COPD-12: All incident COPD patients with a follow-up¹¹ of 12 months since index date
- COPD-24: All incident COPD patients with a follow-up of 24 months since index date
- COPD-36: All incident COPD patients with a follow-up of 36 months since index date
- COPD DMP-FULL DATA: All incident COPD patients with available DMP data (at least one entry during 3 months after index date¹²) and a follow-up of up to 54 months.
- COPD DMP-12: All incident COPD patients with available DMP data (at least one entry during 3 months after index date) and a follow-up of 12 months since index date

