- COPD DMP-24: All incident COPD patients with available DMP data (at least one entry during 3 months after index date) and a follow-up of 24 months since index date
- COPD DMP-36: All incident COPD patients with available DMP data (at least one entry during 3 months after index date) and a follow-up of 36 months since index date.

⁹ Prescription of systemic/oral corticosteroids (SCS/OCS) will not be considered as exclusion criteria

¹⁰ Please note that this samples will not include patients with at least one confirmed inpatient or two confirmed outpatient diagnoses of asthma (ICD-10: J45.-) by pneumologists after the incident COPD diagnosis (index diagnosis) during the follow-up period. Those patients will be described separately.

[figure not shown]
¹¹ Time since patient-individual index date until 30/06/2018; patients who died within this period will not be excluded from the analysis

¹² So far it is unknown how many patients were included in the DMP directly after incident diagnosis and for how many patients an entry in the first months after diagnosis will be available. Thus, depending on the pattern that will be observed in the data, the restriction „at least one entry during the 3 months after index date“ might be extended to „at least one entry during the 6/12 months after index date“.

Figure 3

Baseline period, inclusion period, follow-up period for different study samples

(note: for time to event analyses, COPD-full data sample (with full follow-up times) will be applied). DMP: disease management program (refers to the subsample of patients who participate in the COPD DMP and thus provide more detailed data)

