9.3.2.2 Secondary outcomes

First Secondary

Comparison of initial drug treatment with treatment guidelines

Comparison of real-world treatment of patients with guidelines will be done based on two samples: COPD-12 and COPD DMP-12. Assessment will generally be done for two time points:

- For all patients at index date (+ 4 weeks)
- For patients who received a triple combination (LABA+LAMA+ICS) at first day of triple therapy prescription.

Prescription patterns will be compared with German treatment guideline recommendations. Here, the 2018 S2 guideline [1] will be used (sensitivity analysis: 2012 guideline, which is an updated version of the 2006 guideline [2]). Obviously, as patients are only observed until mid of 2018, it cannot be expected that they were treated in line with the 2018 S2 guideline. However, this analysis describes potential needs to adapt the current treatment of the patients in the future, and is as such important for preparation of later initiatives to optimize the treatment of the patients.

Based on claims data only, assessment of the severity of the COPD disease for COPD patients is hardly possible. The reason is that neither FEV₁ data nor symptoms' data as measured by the COPD assessment test (CAT) or the Modified Medical Research Council (mMRC) are available in a claims dataset. So, for the comparison of the real-world treatment with 2018/2012 guideline recommendations, based on sample COPD-12, the following analyses will be done:

- COPD-12, at index date
 - Based on the inclusion criteria, an incident COPD patient did not experience any exacerbation in the previous 12 months, as no such diagnosis was documented. So, the initial treatment with long-acting bronchodilators should generally not include use of ICS (both guidelines). Moreover, based on the 2012 guideline, a therapy with long-acting bronchodilators should start with either a LAMA or a LABA, but not with a combination of them.

So, based on these criteria, the following percentages will be reported:

- Percentage of patients not treated in line with 2018 guideline
 - Therapy at index date includes ICS
- Percentage of patients not treated in line with 2012 guideline
 - Therapy at index date includes ICS or a LABA/LAMA combination or triple therapy of LABA+LAMA+ICS¹⁶
- COPD-12, at first date of an observed LABA+LAMA+ICS combination, which is not the index date

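### Footnote 1 says COPD patients with an asthmatic component are excluded, but Section 9.2 removes only some asthma coded after index, so ICS in those retained counts as guideline non-adherence

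*Combined protocol and SAP*

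**What the plan says.** Footnote 1 in Section 4 (Abstract) makes two statements: "ICS is recommended by the guideline for COPD patients with an asthmatic component", and "Based on inclusion/exclusion criteria as applied in this study, these patients will be excluded from analysis".

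The pre-index criterion, given in the abstract and in Section 9.2, concerns COPD codes and COPD drugs: "Patients should not have received any COPD diagnosis (ICD-10 J44.-) or any COPD-associated medication" in the 12 months before index. It does not mention asthma. Footnote 9 adds an exemption from the drug washout: "Prescription of systemic/oral corticosteroids (SCS/OCS) will not be considered as exclusion criteria".

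The only asthma rule is in Section 9.2. Patients with one confirmed inpatient J45 diagnosis, or two confirmed outpatient ones "by pneumologists after the incident COPD diagnosis (index diagnosis) will be separately observed". Footnote 10 takes the same patients out of the analysis samples, again for diagnoses made "by pneumologists after the incident COPD diagnosis (index diagnosis) during the follow-up period".

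Section 9.3.1 lists asthma (J45) among the baseline comorbidities to be tabulated for all samples. A patient qualifies with one confirmed inpatient diagnosis, or two confirmed outpatient diagnoses in different quarters, from any physician.

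Section 9.3.2.2 (First Secondary) assesses all COPD-12 patients at index plus 4 weeks. From the absence of a documented exacerbation in the previous 12 months it concludes: "So, the initial treatment with long-acting bronchodilators should generally not include use of ICS (both guidelines"). The 2018 criterion for being out of line is any ICS in the index therapy, and ICS also triggers the 2012 criterion. Table 4 adds comparisons of patients in line and not in line, and a multivariable logistic regression on guideline treatment.

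**The concern.** Footnote 1 gives the reason why ICS at index may be scored as non-adherence without exception: the one group for whom it says ICS is recommended is supposed to be absent. If part of that group is present, treatment that the plan calls recommended is counted as a departure from the guideline, and a reader of footnote 1 would not suspect it.

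The affected percentages answer the first secondary objective. The same classification is the outcome of the planned regression. If baseline asthma is among the covariates (the visible text does not list them), it could appear associated with non-adherence simply because of how the outcome is defined. A large sample does not help, because a narrow confidence interval says nothing about misclassification.

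There is a second, related issue. Footnote 10 uses diagnoses made during follow-up to decide who belongs to a sample that is assessed at index.

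**Working it through.** **Step 1. Who is removed and who stays.** The asthma rule (Section 9.2, footnote 10) is set against the baseline flag (Section 9.3.1). All rows assume no Supplemental Table 2 drug in the 12 months before index, apart from the exempt systemic/oral corticosteroids.

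| J45 coding | Removed from COPD-12? | Caught by the baseline flag? |
|---|---|---|
| Any history, plus one inpatient or two pneumologist outpatient codes after index | Yes | Not relevant |
| Before or at index, meets the comorbidity rule, post-index rule not met | No | Yes |
| Before or at index, one outpatient code only, post-index rule not met | No | No |
| Only after index, by other physicians or once by a pneumologist | No | No |

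The last three rows stay in COPD-12, and any ICS within index plus 4 weeks is scored as not in line.

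**Step 2. Is there a visible remedy?** The sensitivity analyses in Section 9.3.2.2 use fifth-level COPD codes and disease management program (DMP) data; neither concerns asthma. Section 9.11 divides the sample by follow-up and DMP availability only, and item 10.3 of the ENCePP checklist answers No to stratified analyses. The baseline table will show how many patients have J45, but not the guideline percentage without them.

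**Step 3. Possible size.** The plan states no figure for this percentage, so there is nothing to reproduce. Let a be the retained share with J45, p1 their ICS share at index, and p0 the ICS share in the rest. None of the three is in the documents.

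- Reported share: R = (1 − a) × p0 + a × p1.
- Share without these patients: p0.
- Difference: R − p0 = a × (p1 − p0).

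With N = 40,000 (Section 9.5 expects more than this), the difference in percentage points is:

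| Assumed a | Patients | p1 − p0 = 10 | 20 | 40 |
|---|---|---|---|---|
| 1% | 400 | 0.1 | 0.2 | 0.4 |
| 2% | 800 | 0.2 | 0.4 | 0.8 |
| 5% | 2,000 | 0.5 | 1.0 | 2.0 |

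In patients, the corners are 40,000 × 0.01 × 0.10 = 40 and 40,000 × 0.05 × 0.40 = 800 more flagged than at the rate p0.

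**Step 4. Against sampling error.** The largest 95% half-width, at a share of 50%, is 1.96 × √(0.25 / 40,000) = 0.49 points. The shift equals it at:

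- a = 0.49/10 = 4.9% (1,960 patients) for a 10-point difference;
- a = 0.49/20 = 2.45% (980 patients) for 20 points;
- a = 0.49/40 = 1.225% (490 patients) for 40 points.

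At a = 1% the shift stays below the half-width for all three differences.

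**The case against.** The strongest case is that footnote 1 is largely implemented and the remainder is small. The asthma rule stands directly before the definition of the data sets, and footnote 10 applies it. The washout covers SABA, LABA, ICS and ICS+LABA, so asthma treated with these drugs in the year before index is already out. What remains is J45 without any such drug for a year that also misses the post-index rule. The documents do not define an asthmatic component, so whether these patients have one is unknown. All of this stands, and it limits the size. It does not make footnote 1 true as written.

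It can also be said that other parts of the plan cover the point. Table 4 compares patients in line and not in line; if J45 is among the characteristics compared, the percentage without baseline J45 follows by arithmetic. But the characteristics are not listed, and a regression on a misclassified outcome is no remedy. Section 9.9 concedes that reasons for prescribing are unavailable, but that general limitation does not correct a specific statement about who is excluded. The conclusion on initial treatment is hedged with a word meaning as a rule, but the reported criterion has no hedge. Some sections are redacted, so a hidden asthma analysis cannot be ruled out.

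Three stronger readings are tempting:

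- A reader might infer that the exclusion window for COPD-12 runs from 12 to 54 months, because footnote 11 explains follow-up as "Time since patient-individual index date until 30/06/2018". Sections 9.3.2.1 and 9.3.2.2 tie COPD-12 to 12 months, so the documents lean that way and only an explicit statement is missing.
- A reader might infer a contradiction when the index diagnosis is an inpatient exacerbation (J44.1): ICS at index is flagged, yet later triple therapy after such an admission is not. The documents do not support this. The plan's own Figure 1 lists no ICS for patients not pre-treated after a hospitalised exacerbation, and the two rules concern different time points. What remains is wording: whether the phrase separating later triple therapy from the index date also covers the 4-week window.
- A reader might infer a bias of many points. That requires a large retained share, which the washout and footnote 10 work against.

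**Conclusion.** The mismatch is certain from the text. Footnote 1 claims an exclusion that Section 9.2 and footnote 10 carry out only for certain diagnoses after index. Following the plan as written, ICS at index in the retained J45 patients is scored as non-adherence to both guidelines, and the visible analyses do not separate these patients.

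The numerical effect is unknown. The 0.1 to 2.0 points is an illustration under assumed inputs, and an upward shift requires ICS use at index to be higher in J45 patients than in the rest (p1 > p0). The effect may be below sampling error. The illustration sizes one retained share; it does not estimate separately the patients whose asthma is coded only after index. J45 is used because it is the plan's own asthma marker.

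This should be fixed before the analysis, because footnote 1 is inaccurate and the remedy is cheap. It does not show that the guideline comparison is invalid, and it implies no view on whether ICS was appropriate in any patient.

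**What to change.** 1. Reconcile footnote 1 with Section 9.2 and footnote 10, and say what stands for an asthmatic component in this analysis.

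2. Report the index-date guideline percentages, and the logistic regression in Table 4, with and without patients who have J45 before or at index, using the comorbidity flag already derived for Section 9.3.1. As a further sensitivity analysis, also separate patients with any J45 code after index that does not meet footnote 10, since the baseline flag misses them.

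3. Show the index-date percentages once more with the footnote 10 patients put back in, because their removal depends on follow-up. State that the COPD-12 exclusion window is 12 months, if that is what is intended.

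4. As a clarification, say whether the later triple-therapy assessment leaves out only the index day or the whole 4-week window. The choice is the authors'.

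The cost is a few lines of text and one or two extra table columns. Two drawbacks remain: J45 is only a proxy for an asthmatic component, and the analysis without these patients has a slightly smaller denominator.

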
 Previous drug treatment in the pre-index period, based on appropriate ATC group level 
 Percentage of patients who received specific treatments (most common 10 treatments as observable for above samples) with at least two prescriptions in the pre-index period. 
Documentation referring to the 12 months follow-up after index date (for patient subgroups: 24 months/36 months follow-up, or complete follow-up period)
 
 For patients with available data resulting from a disease management program (DMP) 
 Weight [kg] (reported MIN, MAX and MEAN during follow-up period) Height [cm] Blood pressure (reported MIN, MAX and MEAN during follow-up period) Non-drug treatment recommendations Exacerbations (number and severity) FEV₁ (reported MIN, MAX and MEAN during follow-up period) Smoking status if applicable Drug treatment with long-acting bronchodilators (incl. separate reporting for respective agent classes beta-agonists, anticholinergics, methylxanthines) Drug treatment with short-acting agents Drug treatment with anti-inflammatory drugs (ICS, PDE-4, macrolides) Top-10 prescribed non-COPD drug therapies (based on ATC codes on appropriate level) 			

Name of company: Boehringer Ingelheim			
Name of finished medicinal product: COPD medication of any type			
Name of active ingredient: COPD medication of any type, ATC code R03			
Protocol date: 16 Oct 2019	Study number: 1237-0092	Version/Revision: 1.0	Version/Revision date: Not applicable

 • Antibiotics for systemic use (based on ATC J02AA) • Antibiotics in combination with corticosteroids (based on ATC D07C) • Systemic/oral corticosteroids (SCS/OCS; based on ATC R01AD02; D07AA01; D10AA02; H02AB04) • All-cause hospitalizations 
 ○ Among them: hospitalizations with COPD as main diagnosis (ICD-10 J44.-) • Among them: hospitalizations with a COPD exacerbation as main diagnosis (ICD-10 J44.1) • Exacerbations as documented by outpatient pneumologists (ICD-10 J44.1) • GP visits and pneumologists' visits and visits to other specialists • Prescription of COPD-associated aids 
 ○ Oxygen therapy • Date of death, if patient died during follow-up period (for censoring and time to event analyses). 			

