7. RATIONALE AND BACKGROUND

In terms of chronic obstructive pulmonary disease (COPD) drug therapy, the current German COPD guideline (S2) [1] recommends a treatment escalation procedure (Figure 1). For incident COPD patients (for the sake of simplicity, newly diagnosed and so far treatment naïve COPD patients will be referred to as “incident COPD patients” in the following), the guideline recommends the following:

- No treatment (low symptom burden) or
- Short-acting beta antagonist (SABA) or short-acting muscarinic antagonist (SAMA) or
- Long-acting beta agonist (LABA) or long-acting muscarinic antagonist (LAMA) or LABA+LAMA.

All other treatments, particularly combination treatments including inhaled corticosteroids (ICS), are only recommended as escalation therapy. However, despite the increasing evidence (e.g. WISDOM study [3], FLAME study [4]), there might exist the view that early use of ICS in the treatment of COPD might be advisable, and might be prescribed in a substantial percentage of COPD-incident patients.

Figure 1 Treatment recommendations with regard to COPD stages, according to German 2018 S2 guideline [1]

Medikamentöse Dauertherapie der COPD	
Symptome - Ausmaß der Lungenfunktions-einschränkungen berücksichtigen	Medikamentöse Therapie
Wenig (z. B. CAT < 10) GOLD Gruppe A	- Keine - SABA + SAMA (initial) - LABA oder LAMA
Viel (z. B. CAT \geq 10) GOLD Gruppe B	- LABA oder LAMA - LABA + LAMA
Exazerbationen > 1 oder Exazerbation mit Hospitalisierung GOLD Gruppen C und D	
Nicht vorbehandelt	LAMA oder LAMA + LABA
Vorbehandelt	LAMA + LABA
Eskalation/Wechsel	 LABA + ICS → LAMA + LABA + ICS
	\pm Roflumilast (Phänotyp chronische Bronchitis)

Currently, knowledge on real world treatment of incident COPD patients in Germany is sparse, in particular regarding the frequency of different drug therapy prescriptions and the frequency of early therapy escalation including ICS. With the current analyses, we aim to emphasize the central role of LAMA/LABA therapy in COPD and importance of treatment guideline adherence.

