Supplemental Table 2: COPD medications available in the German market

Medication class	Agents	ATC-Codes
SABA	Salbutamol	R03AC02
	Terbutaline	R03AC03
	Fenoterol	R03AC04; R03CC04
	Reprotoerol	R03CC14; R03AC15
LABA	Salmeterol	R03AC12
	Formoterol	R03AC13
	Indacaterol	R03AC18
	Olodaterol	R03AC19
	Bambuterol	R03CC12
	Clenbuterol	R03CC13
LABA-combi	Clenbuterol, combinations	R03CC63
SABA-combi	Fenoterol and sodium cromoglycate	R03AK03
	Salbutamol and sodium	R03AK04
	Reprotoerol and sodium	R03AK05
ICS+LABA	Salmeterol and fluticasone	R03AK06; R03AK61
	Formoterol and budesonide	R03AK07; R03AK28;
	Formoterol and beclometasone	R03AK08; R03AK27;
	Vilanterol and fluticasone furoate	R03AK10
	Formoterol and fluticasone	R03AK11
SABA+SAMA	Fenoterol and ipratropium bromide	R03AL01
	Salbutamol and ipratropium	R03AL02
LABA+LAMA	Vilanterol and umeclidinium	R03AL03
	Indacaterol and glycopyrronium	R03AL04
	Formoterol and aclidinium bromide	R03AL05
	Olodaterol and tiotropium bromide	R03AL06
ICS	Beclometasone	R03BA01; R01AD01
	Budesonide	R03BA02; R01AD05
	Fluticasone	R03BA05; R01AD08
SAMA	Ipratropium bromide	R03BB01; R01AX03
LAMA	Tiotropium bromide	R03BB04
	Aclidinium bromide	R03BB05
	Glycopyrronium bromide	R03BB06
	Umeclidinium	R03BB07
LAMA+LABA+ICS	Glycopyrronium and Formoterol	R03AL09

Medication class	Agents	ATC-Codes
Methylxanthine	Theophylline	R03DA04
	Aminophylline	R03DA05
PDE-4	Roflumilast	R03DX07
Systemic/oral corticosteroids ¹	Prednisolone	R01AD02
	Methylprednisolone	D07AA01; D10AA02;

¹for exacerbations

Supplemental Table 3: Calculation of the Charlson Comorbidity Index (CCI)

No	Comorbidity	Charlson Score	ICD-10 Code
1	Coronary artery disease	1	I20.-, I21.-, I22.-, I23.-, I24.-, I25.-
2	Congestive heart failure	1	I11.-, I50.-
3	Peripheral vascular disease	1	I73.-, I74.-, I77.-
4	Cerebrovascular disease	1	G45.-, G46.-, I6.-
5	Dementia	1	F00.-, F01.-, F02.-, F03.-, G30.-
6	Chronic pulmonary disease	1	J4.-, J6.- w/o J67.-, J68.-, J69.-
7	Connective tissue disorder	1	M05.-, M06.-, M07.-, M08.-, M3.-
8	Peptic ulcer disease	1	K25.-, K26.-, K27.-, K28.-
9	Mild liver disease	1	B18.-, K70.-, K73.-, K75.-
10	Diabetes mellitus without complications	1	E109.-, E119.-, E129.-, E139.-, E149.-
11	Hemiplegia	2	G81.-, G82.-
12	Moderate or severe renal disease	2	N17.-, N18.-, N19.-
13	Diabetes mellitus with end-organ damage	2	E10.-, E11.-, E12.-, E13.-, E14.- w/o [No 10]
14	Tumor without metastases, leukemia, lymphoma, multiple myeloma	2	C% w/o [No 16]

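### The 2018 index-date guideline criterion tests only for ICS, so methylxanthine or roflumilast starts without ICS count as in line, against the plan's own guideline summary

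*Combined protocol and SAP*

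**What the plan says.** Section 7 lists the options for a newly diagnosed, untreated patient and then states: "All other treatments, particularly combination treatments including inhaled corticosteroids (ICS), are only recommended as escalation therapy". The abstract (section 4) gives the same list, which ends with "LABA or LAMA or LABA+LAMA". In Figure 1, the entry "Roflumilast (Phänotyp chronische Bronchitis" is printed after the escalation/switch row.

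Section 9.3.2.2 turns this into two rules, applied to all COPD-12 patients at index date plus 4 weeks.

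- Not in line with 2018: "Therapy at index date includes ICS".
- Not in line with 2012: "Therapy at index date includes ICS or a LABA/LAMA combination or triple therapy of LABA+LAMA+ICS".

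The rationale given for the 2012 rule is that "a therapy with long-acting bronchodilators should start with either a LAMA or a LABA, but not with a combination of them".

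Supplemental Table 2 lists "Theophylline" (R03DA04) and aminophylline (R03DA05) as methylxanthines, and roflumilast (R03DX07) as a PDE-4 inhibitor. In the abstract's variable list, long-acting bronchodilators are to be reported by "respective agent classes beta-agonists, anticholinergics, methylxanthines"; PDE-4 inhibitors appear there as anti-inflammatory drugs.

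Table 4 in section 9.7.1 reports the proportion treated in line, compares patients in line with those not in line, and fits a multivariable logistic regression to that outcome.

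**The concern.** The guideline summary is exhaustive: whatever is not on the list is escalation, with ICS combinations named as the leading example and not as the limit. The 2018 rule keeps only that example. Because Table 4 defines no third category, anyone the rule does not flag is in line. A patient whose first treatment is theophylline, aminophylline or roflumilast without ICS would therefore be reported as treated according to the 2018 guideline, although the plan's own text places that start under escalation.

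At stake is the first secondary objective. The reported percentage would not measure what sections 4 and 7 say adherence is, and the regression would model the same mismatched outcome.

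**Working it through.** The plan states no figure for this quantity, so the check compares the rules with the summary and then shows how the percentage depends on the unknown frequency.

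**Step 1: which regimens does the gap affect?** Take seven drug classes: SABA, SAMA, LABA, LAMA, ICS, methylxanthine and PDE-4 inhibitor. They form 2^7 = 128 possible combinations, including no drug. By the section 4 and 7 summary, any combination with a class other than SABA, SAMA, LABA or LAMA is escalation.

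- 2018 rule (flag if ICS is present). Combinations that the summary calls escalation but the rule leaves in line have no ICS and at least one of methylxanthine and PDE-4 inhibitor: 2^4 × 3 = 48.
- 2012 rule (flag if ICS, or LABA with LAMA, is present), set against the same summary. The 4 of 16 bronchodilator subsets that hold both LABA and LAMA drop out: (16 − 4) × 3 = 36.

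These are counts of regimen types, not of patients. They show that the mismatch arises only from these two classes and only without ICS.

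| Start at index | 2018 rule | 2012 rule | Sections 4 and 7 |
|---|---|---|---|
| Methylxanthine alone | in line | in line | escalation |
| Roflumilast alone | in line | in line | escalation |
| LAMA + methylxanthine | in line | in line | escalation |
| LABA + LAMA + roflumilast | in line | not in line | escalation |
| LABA + ICS + methylxanthine | not in line | not in line | escalation |

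**Step 2: can such starts occur in the cohort?** Yes. Section 9.2 excludes patients with a Supplemental Table 2 drug in the 12 months before index (systemic corticosteroids excepted). A methylxanthine or roflumilast prescription at index is then a new start relative to those 12 months. Nothing removes it afterwards.

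**Step 3: effect on the 2018 percentage.** Let q be the share of patients whose index (+4 weeks) therapy contains a methylxanthine or roflumilast but no ICS. If the rule followed the summary, the not-in-line percentage would rise by q. The documents do not give q. Section 9.5 expects more than 40,000 incident patients; 40,000 serves here as an illustrative denominator.

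| Assumed q | Patients moved (q × 40,000) | Rise in 2018 not-in-line figure |
|---|---|---|
| 0.5% | 200 | 0.5 points |
| 1% | 400 | 1 point |
| 2% | 800 | 2 points |
| 5% | 2,000 | 5 points |

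For 2012 the same reclassification would move at most these numbers, because starts that also contain LABA with LAMA are already flagged.

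**Step 4: is the gap closed elsewhere?** The visible sensitivity analyses in section 9.3.2.2 use severity subcodes and DMP data; neither adds these classes.

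**The case against.** The strongest reply is that the rule is a deliberately narrow proxy. Section 9.3.2.2 admits that severity can hardly be assessed from claims, frames its test around initial treatment with long-acting bronchodilators, and prints the criterion beside each percentage. On that view the conflict is only with a background sentence. Part of this stands: a reader can see what was tested, and PDE-4 inhibitors lie outside the long-acting bronchodilator class, so roflumilast alone is the weaker case under that wording. It does not remove the mismatch. All patients are scored, the abstract places methylxanthines inside the class, and detecting these drugs needs prescription codes only, not severity data.

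A second reply is that Figure 1 names roflumilast but neither methylxanthine, so the status of those two rests on the catch-all sentence. That is correct, but the sentence is the plan's own.

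A third is that use of these drugs is visible in the follow-up drug tables and in resource use. Those cover follow-up periods, not the index window, so they help only in part.

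A reader might also infer that non-adherence is understated for both guidelines. The documents do not support this for 2012. Section 7 attributes the escalation sentence to the current guideline, and the requirement to begin with a LAMA or a LABA can be read as contrasting single with dual therapy. Moreover, section 9.3.2.2 says that the 2012 guideline also recommended triple therapy at FEV1 below 50%, yet the index-date rule flags every triple start. That pushes the 2012 figure the other way.

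**Conclusion.** The point holds for 2018. The index-date criterion does not match the summary in sections 4 and 7, and methylxanthine or roflumilast starts without ICS are counted as in line. Measured against the plan's own text, this component can only lower the 2018 not-in-line percentage, by q. The size is unknown: the 0.5% to 5% range is an assumption, and the effect may be negligible.

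For 2012, which the plan labels a sensitivity analysis, the gap is arguable and the net direction of error is not established.

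It is also tempting to say that the regression coefficients will be diluted. That would be expected only if the misclassification were unrelated to the covariates, and the documents give no basis for assuming so. What can be said is that the regression would use an outcome that differs from the stated definition of adherence.

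Severity is minor to moderate. The measure can be interpreted as an ICS criterion, but not, as it stands, as adherence in the sense of sections 4 and 7.

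**What to change.** Reconcile section 9.3.2.2 with sections 4 and 7 in one of two ways. Which reading of the guidelines is right is for the sponsor to decide.

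1. Add methylxanthines (R03DA04, R03DA05) and the PDE-4 inhibitor (R03DX07) to the 2018 not-in-line definition, and to the 2012 definition only if the sponsor confirms that guideline's position. Report each component separately so that the ICS-only percentage stays visible, and use the reconciled outcome in the logistic regression.
2. Keep the present rules, relabel the measure as ICS (and, for 2012, LABA/LAMA) use only, revise the summary in sections 4 and 7, and report methylxanthine and PDE-4 starts at index separately.

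Under either option, state how other Supplemental Table 2 products outside the list, such as the SABA-cromoglycate combinations, are scored.

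The cost is a few lines of wording. The codes are already in Supplemental Table 2, which the pre-index exclusion uses. The final extraction list is not among the documents and should be checked for them.
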